5.3 Lifestyle restrictions

5.3.1 Meals and dietary restrictions

Patients enrolled in the study should adhere to the following fasting conditions for the duration of the study. Any event likely to interfere with the objectives of the study will be communicated to the Investigator and reported without delay to the Sponsor.

1. Patients should eat and drink only the standardised meals and drinks provided according to the study centre's standard practice during their entire stay at the study centre each treatment visit. Meals should not include any xanthine-containing compounds (ie, caffeine) or grapefruit-containing foods or beverages. No food intake will be allowed between meals.
2. On Day 1, Day 8, and Day 14 of each treatment period, patients will be required to undergo an 8-hour overnight fast before IP administration and will maintain a fasted condition for an additional 4 hours following IP administration on Day 1 and Day 14. On Day 8 a fasted condition of 1 hour after IP administration should be

observed. During other treatment days, there are no fasting requirements prior to IP administration.

3. Patient should fast for 4 hours before i-STAT (potassium and glucose measurements) and for 8 hours before routine safety laboratory testing. During patients' stays at the study centre, standardised meals will be served according to the study centre's standard practice.
4. Intake of water will not be allowed 1 hour prior to administration of the IP and 1 hour post-administration of the IP on Day 1, Day 8, and Day 14 of each treatment period.
5. Patients must abstain from consuming any of the following:
 - Poppy seeds (eg, found in bread) from time of consent until the final Follow-up Visit at the end of the study.
 - Grapefruit or grapefruit juice, or Seville orange (also called bitter orange, including marmalade) consumption from 48 hours prior to administration of the IP at Visit 3 until the final Follow-up Visit at the end of the study.

5.3.2 Caffeine, alcohol, and tobacco

1. Patients must abstain from any of the following:
 - Alcohol from 72 hours before each visit to the study centre and during the entire stay at the study centre.
 - Smoking should be avoided for 1 hour prior to the pulmonary function tests.
 - Energy drinks containing taurine or glucuronolactone (eg, Red Bull) from 72 hours prior to administration of the IP at Visit 3 until the Follow-up Visit at the end of the study.
 - Caffeine-containing food and drinks for 24 hours prior to each visit to the study centre and during the entire stay at the study centre. Decaffeinated drinks will be acceptable to be consumed during the study.

5.3.3 Activity

1. Patients should avoid exposure to dust or polluted air for at least 1 hour before conducting any respiratory procedures.
2. Patients must abstain from strenuous physical activity, which is not within the patient's normal daily routine, from 72 hours before the Screening Visit until the Follow-up Visit at the end of the study.

5.3.4 Medication and other restrictions

1. Salbutamol should be withheld at least 6 hours before each visit where spirometry is performed up to the last spirometry procedure on that visit. However, patients are permitted to use salbutamol if its use is absolutely necessary during the visit, and with the approval of the Investigator.
2. Ipratropium should be withheld at least 8 hours before Visits 3, 6 and 9 and during all treatment periods. This medication is to be used during the run-in and wash-out periods.
3. Patients must abstain from any of the following:
 - Blood or plasma donation from Screening (Visit 1) until 3 months after the Follow-up Visit at the end of the study.
 - Scheduled in-patient surgery or hospitalisation during the course of the study (patients are not required to abstain from emergency treatment).
 - Restrictions on medications (prescribed or over-the-counter products) are defined in Section 6.5.

5.4 Screen failures

Screening failures are defined as patients who signed the ICF to participate in the clinical study but are not subsequently randomly assigned to study treatment. A minimal set of screen failure information is required to ensure transparent reporting of screen failure patients to meet the Consolidated Standards of Reporting Trials (CONSORT) publishing requirements and to respond to queries from regulatory authorities. Minimal information includes demography, screen failure details, eligibility criteria, and any SAE.

Individuals may be rescreened only if the patient has not failed any assessment but was not randomised within the screening window (28 days of their first assessment). Individuals who do not meet the eligibility criteria (despite the repeated tests) will be screen failed. Repetition of the entire Screening Visit is not allowed. Rescreened patients should be assigned the same patient number as for the initial screening. However, rescreening should be documented so that its effect on study results, if any, can be assessed.

These patients should have the reason for study withdrawal recorded in the electronic Case Report Form (eCRF).

6. STUDY TREATMENTS

Study treatment is defined as any investigational product(s) (including marketed product comparator and placebo) or medical device(s) intended to be administered to a study participant according to the study protocol. Study treatment in this study refers to AZD8871, Anoro[®] Ellipta[®], and placebo.

6.1 Treatments administered

6.1.1 Investigational products

Table 3 Study Treatments

	Treatment 1	Treatment 2	Treatment 3	Treatment 4
Study treatment name:	AZD8871 (as saccharinate) inhalation powder in SD3FL DPI	Anoro [®] Ellipta [®] (umeclidinium [UMEC]/vilanterol [VI])	Placebo to AZD8871 in SD3FL DPI	Placebo to Anoro [®] Ellipta [®]
Dosage formulation:	600 µg	Predispensed: UMEC 62.5 µg, VI (as trifenate) 25 µg. Delivered dose: UMEC 55 µg, VI (as trifenate) 22 µg.	N/A	N/A
Route of administration	Oral inhalation	Oral inhalation	Oral inhalation	Oral inhalation
Dosing instructions:	1 inhalation per day	1 inhalation per day	1 inhalation per day	1 inhalation per day
Packaging and labelling	Study treatment will be provided in individual patient kit labelled with study-specific label. Each kit will be labelled in accordance with Good Manufacturing Practice (GMP) Annex 13 and per country regulatory requirement. Label text will be translated into local language. The planned dose of AZD8871, Anoro [®] Ellipta [®] , or placebo will be administered via multi-dose DPI device. Each DPI device will be packed in an aluminium pouch including desiccant. Further information will be provided in the Investigator drug manual. For training purposes, each patient will receive an empty DPI device for SD3FL (a variant of the commercially available Genuair [®] or Pressair [®] DPI) that will be used on Visit 3, 6 and 9, if considered necessary.			

DPI: Dry powder inhaler; UMEC: umeclidinium; VI: vilanterol

6.2 Preparation/handling/storage/accountability

Study treatment will be provided in individual patient kit labelled with study-specific label. All IP should be kept in a secure place under appropriate storage conditions. The label on the IP specifies the appropriate storage.

The Investigator or designee must confirm appropriate temperature conditions have been maintained during transit for all study treatment received and any discrepancies are reported and resolved before use of the study treatment.

Only patients enrolled in the study may receive study treatment and only authorised site staff may supply or administer study treatment. All study treatments must be stored in a secure, environmentally controlled, and monitored (manual or automated) area in accordance with the labelled storage conditions with access limited to the Investigator and authorised site staff.

The Investigator, institution, or the head of the medical institution (where applicable) is responsible for study treatment accountability, reconciliation, and record maintenance (ie, receipt, reconciliation, and final disposition records).

To allow drug reconciliation and dispensation control, research personnel will record patient ID on the labels of the patient kit, every period kit dispensed, as well as on the aluminium pouch labels and inhaler labels.

The manufacturing, labelling, packaging and release of AZD8871 and placebo to AZD8871 will be conducted following GMP by AstraZeneca. Batch numbers will be indicated in the Clinical Study Report (CSR).

Further guidance and information for the final disposition of unused study treatment are provided in the Investigator drug manual.

6.3 Measures to minimise bias: randomisation and blinding

PAREXEL will be responsible for generating the randomisation scheme through the AZRand programme. The randomisation schedule will describe the link between the randomly assigned sequences of 3 treatments to each randomisation number.

At Visit 3, approximately 72 patients will be randomly assigned to 1 of the 6 possible treatment sequences, according to a William's design for crossover studies and using a balanced 1:1:1:1:1:1 randomisation ratio. Thus, 12 patients will be assigned to each treatment sequence (Table 4). To ensure random allocation, each patient will be given the IP bearing the lowest available randomisation number at the site.

Table 4 Treatment sequences

		Treatment Period 1	Treatment Period 2	Treatment Period 3
Sequence A (n=12)	AZD8871	600 µg	Placebo	Placebo
	Anoro® Ellipta®	Placebo	55 µg / 22 µg	Placebo
Sequence B (n=12)	AZD8871	600 µg	Placebo	Placebo
	Anoro® Ellipta®	Placebo	Placebo	55 µg / 22 µg
Sequence C (n=12)	AZD8871	Placebo	600 µg	Placebo
	Anoro® Ellipta®	55 µg / 22 µg	Placebo	Placebo
Sequence D (n=12)	AZD8871	Placebo	Placebo	600 µg
	Anoro® Ellipta®	55 µg / 22 µg	Placebo	Placebo
Sequence E (n=12)	AZD8871	Placebo	600 µg	Placebo
	Anoro® Ellipta®	Placebo	Placebo	55 µg / 22 µg
Sequence F (n=12)	AZD8871	Placebo	Placebo	600 µg
	Anoro® Ellipta®	Placebo	55 µg / 22 µg	Placebo

The Investigator(s) will:

1. Obtain signed informed consent from the potential patient before any study-specific procedures are performed.
2. Assign each patient a unique patient identification number. This number will be composed of 2 parts: the first 4 digits (fixed) representing the site identifier. The next 3 digits (ascending) which will be assigned sequentially within each site, starting with 001. The patient identification number will be used to identify the patient throughout the study and will be recorded in the eCRF.
3. Determine patient eligibility; see Section 5.
4. For patients fulfilling the eligibility criteria at Visit 3, the Investigator will assign a unique randomisation number following chronological ascending order.

Randomisation codes will be assigned strictly sequentially as patients become eligible for randomisation. The randomisation numbers will be grouped in blocks at an overall level. The block size will not be communicated to the Investigators.

All patients will be centrally assigned to randomised study treatment using an interactive voice/web response system (IVRS/IWRS). Before the study is initiated, the telephone number and call-in directions for the IVRS and/or the log-in information and directions for the IWRS will be provided to each site.

Randomisation data will be kept strictly confidential. The randomisation list will only be provided to AstraZeneca personnel responsible for study IP preparation and to Covance Bioanalytical group responsible for PK analyses.

When the study is completed and the data verified and locked and the populations defined, the randomisation codes will be made available for data analysis.

If a patient withdraws from the study, then his/her enrolment/randomisation code cannot be reused. Withdrawn patients will not be replaced.

This study will be performed in a double-blind manner. All IPs will be supplied in identical packaging to enable double-blind conditions.

AZD8871 and Anoro[®] IPs will be provided in the SD3FL (a variant of the commercially available Genuair[®] or Pressair[®] DPI) and Ellipta[®] DPI devices, respectively. Placebos will be provided in both the SD3FL and Ellipta[®] DPI devices with the same external appearance and containing lactose monohydrate; the Ellipta[®] placebo DPI device will also contain Magnesium Stearate.

For each treatment period patients will be provided with one SD3FL DPI device and one Ellipta[®] DPI device for daily administration of one of the 3 following combinations: AZD8871-placebo, placebo-Anoro[®], or placebo-placebo.

Supplies of salbutamol and ipratropium will be open-label.

The IVRS/IWRS will provide to the Investigator(s) or pharmacists the kit identification number to be allocated to the patient at the dispensing visit.

Routines for this will be described in the IVRS/IWRS user manual that will be provided to each centre.

The randomisation code should not be broken except in medical emergencies when the appropriate management of the patient requires knowledge of the treatment randomisation. The Investigator documents and reports the action to AstraZeneca, without revealing the treatment given to the patient to the AstraZeneca staff.

AstraZeneca retains the right to break the code for SAEs that are unexpected and are suspected to be causally related to an IP and that potentially require expedited reporting to regulatory authorities. Randomisation codes will not be broken for the planned analyses of data until all decisions on the evaluability of the data from each individual patient have been made and documented.

The IVRS/IWRS will be programmed with blind-breaking instructions. In case of an emergency, the Investigator has the sole responsibility for determining if unblinding of a patient's treatment assignment is warranted. Patient safety must always be the first consideration in making such a determination. If the Investigator decides that unblinding is warranted, the Investigator is asked to contact the Sponsor prior to unblinding a patient's

treatment assignment unless this could delay emergency treatment of the patient. In this case, the Sponsor must be notified within 24 hours after breaking the blind. The date and reason that the blind was broken must be recorded in the source documentation and eCRF, as applicable. Study unblinding should not occur until database lock and all decisions on the evaluability of the data from each individual patient have been made and documented.

6.4 Treatment compliance

Investigators will record patients' IP intake in the eCRF during site visits. For IP use between visits, patients will be provided with an e-Diary to record their intake of the IP on a daily basis. Any change from the dosing schedule, dose interruptions, dose reductions, dose discontinuations should be recorded in eCRF.

The Investigational Product Storage Manager is responsible for managing the IP from receipt by the study site until the destruction or return of all unused IP. The Investigator(s) is responsible for ensuring that the patient has returned all unused IP.

6.5 Concomitant therapy

Any treatment taken during the 2 weeks prior to signing of the ICF must be recorded in the Previous and Concomitant Medication eCRF page to ensure proper wash-out of prohibited medications.

Patients will be withdrawn from their usual COPD therapy after signing the ICF and will be maintained on a mono-component ICS therapy, if required. Ipratropium will be provided during run-in and wash-out periods but should be held at least 8 hours before Visits 3, 6 and 9 (before any pulmonary function test) and during all treatment periods. In addition, salbutamol will be provided as rescue medication for the duration of the study.

From the first IP administration, any new treatments taken or any change in ongoing medications during the participation in the study, apart from the IP, will be transcribed onto the corresponding eCRF page by the Investigator or designee.

Patients must be instructed to inform the Investigator of plans to take any new treatment during the participation in the study, including over-the-counter medicinal and herbal products.

In the interest of patient safety and acceptable standards of medical care, patients may be allowed to take any medications not listed as either permitted or not permitted (see below) at the discretion of the Investigator. All treatments must be recorded in the patients' eCRF. Any medication taken for medical reasons deemed acceptable by the Investigator prior to study entry will be continued at the same dose and conditions until completion of the Follow-up Visit.

[Table 5](#) and [Table 6](#) summarise different possible treatments for COPD and other indications which are allowed and prohibited, respectively, with example of medication and applicable restrictions.

Table 5 Restricted medications

Medications:	Usage (including limits for duration permitted and special situations in which it's allowed):
Oral anti-histamines, intranasal corticosteroids and sympathomimetics and intranasal anticholinergics	Allowed but avoid for 24 hours prior and up to 36 hours post-IP dosing at each period
ICSs mono-component	Allowed but if taken, dosage and regimen must be stable during the study duration. Avoid for 12 hours prior to any spirometry test
Rescue medication: Salbutamol 100 µg	Allowed but avoid for 6 hours prior to any spirometry test for the study
Ipratropium 20 µg × 2 puffs 4 times per day	Mandatory during run-in and wash-out periods but should be held at least 8 hours before Visits 3, 6 and 9 (before any pulmonary function test) and during all treatment periods (until last pulmonary function test at Visits 5, 8 and 11)

ICS=Inhaled corticosteroid.

Table 6 Prohibited medications

Drug Class	Restrictions
ANTICHOLINERGICS	
Oral or parenteral	Wash-out of 72 hours required before Visit 2
Inhaled short-acting, SAMAs	Wash-out of 8 hours required before Visit 2
Inhaled long-acting, LAMAs	Wash-out of 72 hours before Visit 2
B₂-ADRENERGIC AGONISTS	
Inhaled short-acting, SABAs (except Salbutamol rescue medication)	Wash-out of 6 hours before starting first pulmonary function test at each study visit
Inhaled long-acting, LABAs (BID or QD)	BID: Wash-out of 48 hours required before Visit 2
	QD: Wash-out of 7 days required before Visit 2
Oral short-acting	Wash-out of 24 hours required before Visit 2
COMBINATIONS (INHALED)	
Inhaled long-acting LABA/LAMA combinations (BID or QD)	BID: Wash-out of 48 hours required before Visit 2
	QD: Wash-out of 7 days required before Visit 2
LABA + ICS fixed-dose combinations	Stop combination at least 48 hours before Visit 2 and switch to ICS mono-component at Visit 1

Table 6 Prohibited medications

Drug Class	Restrictions
SABA + anticholinergic agent	Wash-out of 72 hours required before Visit 2
CORTICOSTEROIDS	
Continuous oral or parenteral	Wash-out of 6 weeks required before Visit 2
OTHERS	
Methyl-xanthines	Patients with these medications should not be enrolled into the study
Mast cell stabilisers	Wash-out of 5 days required before Visit 2
Leukotriene modifiers	Wash-out of 48 hours required before Visit 2
Selective and non-selective β -blocking agents (oral or topical including eye drops)	Patients with these medication should not be enrolled into the study
Phosphodiesterase IV inhibitors	Wash-out of 4 weeks required before Visit 2
Anti-IgE and anti-IL-5 antibody therapies	Wash-out of 6 months required before Visit 2
Medications that prolong the QT/QTc interval (other than inhaled β_2 agonist) eg, anti-arrhythmics, anti-psychotics and fluoroquinolones	Stable at least 4 weeks prior to Visit 2
“Experimental”, non-approved medications	Wash-out of 3 months before Visit 1
Strong inhibitors of carboxyl esterase 2	Wash-out of 5 days required before Visit 2
Live attenuated vaccine	Wash-out of 30 days before screening
Inactivated vaccine	Wash-out of 7 days before screening or randomisation (Visit 3) Wash-out of 7 days before each treatment period Inactivated vaccines are not allowed during the treatment periods

BID=Twice a day; ICS=Inhaled corticosteroid; IgE=Immunoglobulin E; IL-5=Interleukin-5; LABA=Long-acting β_2 -agonist; LAMA=Long-acting muscarinic antagonist; QD=Once a day; SABA=Short-acting β_2 -agonist; SAMA=Short-acting muscarinic antagonist.

6.5.1 Background medication

The IP will not be given as an “add-on” to another medication or class of medication.

6.5.2 Other concomitant treatment

Other medication other than that described above, which is considered necessary for the patient’s safety and wellbeing, may be given at the discretion of the Investigator and recorded in the appropriate sections of the eCRF.

6.5.3 Rescue medication

The study site will supply salbutamol rescue medication (Table 7) that will be provided by the Sponsor or PAREXEL. Patients will be provided with an e-Diary to collect their daily use of rescue medication during the run-in and treatment periods.

Although the use of rescue medications is allowable at any time during the study, the use of rescue medications should be delayed, if possible, for at least 6 hours before any pulmonary function test. The date and time of rescue medication administration as well as the dosage regimen of the rescue medication must be recorded.

Table 7 Rescue medication

Rescue drug:	Usage:
Salbutamol 100 µg	As needed but avoid for 6 hours prior to any spirometry test for the study

6.6 Dose modification

N/A.

6.7 Treatment after the end of the study

N/A.

7. DISCONTINUATION OF TREATMENT AND SUBJECT WITHDRAWAL

7.1 Discontinuation of study treatment

Patients may be discontinued from IP in the following situations.

- Patient decision. The patient is at any time free to discontinue treatment, without prejudice to further treatment.
- Adverse Event.
- Severe non-compliance with the Clinical Study Protocol.
- Failure to meet randomisation criteria: Violations of inclusion and/or exclusion criteria detected after randomisation. See Section 7.3 for patients not fulfilling inclusion/exclusion criteria but detected after randomisation.
- Lost to follow-up: See Section 7.2 for details.
- Pregnancy: In case of pregnancy the female patient will be immediately discontinued from study treatment.

- Clinical/FEV₁ stability criteria not fulfilled during the treatment periods.
- Development of study-specific withdrawal criteria: These criteria are listed below; in the event that any of these conditions are reported as an AE, then this AE should be reported as the primary reason for discontinuation in the eCRF.
- Withdrawal of consent to the use of donated biological samples.

(a) Vital signs (any time after randomisation; the test must be repeated to confirm that withdrawal criterion has been met)

- Systolic blood pressure (SBP) increase of >40 mmHg from pre-dose at Day 1 of each treatment period AND SBP >180 mmHg at any time within the 12-hour interval after taking study treatment.

(b) Laboratory findings (any time after randomisation; the test must be repeated to confirm that withdrawal criterion has been met)

- Haematologic toxicity defined as 1 or more of:
 - Confirmed leucocyte count $<2.0 \times 10^9/L$.
 - Confirmed neutrophil count $<1.0 \times 10^9/L$.
 - Confirmed platelet count $<75 \times 10^9/L$.
 - Confirmed lymphocyte count $<0.5 \times 10^9/L$.
- Hepatic toxicity defined as 1 or more of:
 - Confirmed alanine aminotransferase (ALT) or aspartate aminotransferase (AST) increase to $>3 \times$ the upper limit of normal (ULN).
 - Confirmed isolated total bilirubin (TBL) increase to $>2 \times$ ULN.
 - Confirmed ALT or AST increase to $>2 \times$ ULN concurrent with an increase in TBL to $>1.5 \times$ ULN.
- Serum potassium, checked within 4 hours post-dose on the days tested, <3.0 mmol/L, will be treated appropriately by the Investigator, and the patient will be withdrawn from study treatment.

(c) ECG (within 4 hours of post-IP dosing; the test must be repeated to confirm that withdrawal criterion has been met):

- Symptomatic bradycardia defined as heart rate <45 bpm or asymptomatic bradycardia defined as resting supine pulse <30 bpm while awake, persisting for at least 10 min.

- Heart rate of >120 bpm and an increase of >40 bpm during the first 4 hours post-dose, persisting for at least 10 min.
- QTcF interval prolongation exceeding >500 ms during the treatment period OR >60 ms change from pre-dose at Day 1 of each treatment period (within 4 hours post-dose), persisting for at least 5 min.

(d) Lung function

- FEV₁ decrease by >20% from pre-dose at Day 1 of each treatment period (ie, before first dose of study treatment) on 2 consecutive spirometry assessments obtained at least 15 min apart AND with associated symptoms of dyspnoea at any time within the first 2-hour interval after taking study treatment.

(e) Moderate to severe COPD exacerbation

- COPD exacerbation of moderate or severe intensity.

Note: A COPD exacerbation is defined as a change in the patient's baseline dyspnoea, cough, and/or sputum (increase in volume or change in colour towards purulence) that lasts ≥ 3 days, is beyond normal day-to-day variations, is acute in onset, and may warrant a change in regular medication. The severity of COPD exacerbations is classified as follows:

- Mild: Exacerbations that do not require systemic steroids or antibiotics and do not result in hospitalisation or death.
- Moderate: Exacerbations that require treatment with systemic steroids and/or antibiotics, and do not result in hospitalisation or death.
- Severe: Exacerbations that result in hospitalisation or death.

(f) Other

- Study cancellation or any other reason not described above.
- Patient withdrawal due to death.

Generally, before discontinuation of a patient from the study, a discussion between Sponsor's Study Physician and Investigator is encouraged, as much as feasible.

See the SoA ([Table 1](#)) for data to be collected at the time of treatment discontinuation and follow-up and for any further evaluations that need to be completed.

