42	Participation in another clinical study with investigational drug or device within the last 30 days or 5 half-lives (whichever is longer) prior to Screening.	Yes ⁺⁺⁺	No	Yes ⁺⁺⁺	No
43	Patient with known human immunodeficiency virus (HIV) infection or chronic hepatitis B or C infection.	Yes	No	No	No
44	Patient did not fulfill fasting requirements on Day 1, 8, and 14 before IP administration and following dose administration.	Yes ⁺⁺	No	No	No
45	Salbutamol not withheld at least 6 hours prior to any spirometry test for the study.	Yes	No	No	No
46	Ipratropium not withheld at least 8 hours before visits 3, 6, and 9 and during all treatment periods.	Yes	No	No	No
47	Patient could not abstain from list in protocol section 5.3	Yes	No	No	No
48	Patient who had 2 or more exacerbations of COPD within the last year prior to Screening	Yes	No	No	No
49	Patient unable to abstain from protocol-defined prohibited medications during the study, in the opinion of the investigator.	Yes ⁺⁺	No	Yes ⁺⁺	No
50	Patient is screening failure, but received study drug.	Yes	Yes	Yes	Yes
51	Incorrect study medication received.	Yes ⁺⁺	No	Yes ⁺⁺	No

Item #	Event description	Excluded from analysis set			
		P-PS	SS	PKS	FAS
52	Incorrect dose of study medication received.	Yes ⁺⁺	No	Yes ⁺⁺	No
53	Patient did not take any IP	Yes ⁺⁺	Yes	Yes ⁺⁺	Yes ⁺⁺
54	IP not taken at the study site at 9:00 AM±2 hours on Day 1 (Visits 3, 6 and 9).	Yes ⁺⁺	No	Yes ⁺⁺⁺	No
55	IP not taken within ±1 hours of dosing time of Day 1 and between 7 AM and 11AM on subsequent days of each treatment period.	Yes ⁺⁺	No	Yes ⁺⁺⁺	No
56	Patient has taken any of the restricted medications on a different regimen than the described in the protocol (Table 5, section 6.5).	Yes ⁺⁺	No	Yes ⁺⁺⁺	No
57	Procedure not performed (missing PK samples to prevent calculation of PK parameters).	No	No	Yes ⁺⁺	No
58	Study assessments (For example cough monitoring, spirometry, CC1 i-Stat, 12 Lead ECG and/or vital signs) are not performed at the scheduled timepoints.	No	No	No	No
59	Missing baseline data for the spirometry (FEV1 main variable)	Yes ⁺⁺	No	No	No
60	FEV1 and FVC measurements performed outside tolerance window	No	No	No	No
61	Fulfilling withdrawal criteria during the study but not withdrawn.	Yes	No	No	No
62	Fatal or life-threatening AE was not reported to the appropriate AstraZeneca representatives within 1 calendar day of initial receipt.	No	No	No	No

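### The QTcF >500 ms withdrawal limb carries two incompatible time windows, and the SBP and potassium criteria each state two without saying which governs

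*Protocol*

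**What the plan says.** Protocol Section 7.1 groups its study-specific withdrawal criteria under lettered headings. Each of the three headings at issue states a time window, and so do the bullets in question.

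- **Blood pressure.** The heading reads "a) Vital signs (any time after randomisation; the test must be repeated to confirm that withdrawal criterion has been met". Its only bullet requires a rise of more than 40 mmHg from the Day 1 pre-dose value together with "SBP >180 mmHg at any time within the 12-hour interval after taking study treatment".
- **Potassium.** The heading reads "b) Laboratory findings (any time after randomisation; the test must be repeated to confirm that withdrawal criterion has been met". The bullet reads "Serum potassium, checked within 4 hours post-dose on the days tested, <3.0 mmol/L", and says that such a patient will be withdrawn from study treatment.
- **QTcF.** The heading reads "c) ECG (within 4 hours of post-IP dosing; the test must be repeated to confirm that withdrawal criterion has been met". The bullet has two limbs. One is "QTcF interval prolongation exceeding >500 ms during the treatment period". The other is a change of more than 60 ms from the Day 1 pre-dose value, which carries its own 4-hour window in parentheses.

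Nothing in Section 7.1 says whether heading or bullet prevails. Section 8.2.4 sends sites to Section 7.1 for the QTcF withdrawal criteria.

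SAP Section 2.2 lists meeting discontinuation criteria without being withdrawn or stopping treatment, as appropriate, among the important deviations. SAP Table 1 item 61, "Fulfilling withdrawal criteria during the study but not withdrawn", excludes the patient from the per-protocol set only. It lacks the marks that limit other exclusions to a timepoint or period, or leave them to the data review meeting.

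**The concern.** A numeric stopping rule should give one answer for one reading. The schedule of activities places blood pressure, ECG and i-STAT potassium readings at times that fall inside one of the stated windows and outside the other. A repeat-confirmed QTcF above 500 ms at the scheduled 24-hour ECG meets the bullet in 7.1(c) and fails the heading.

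Stopping is hard to undo. Temporary discontinuation is not permitted (Section 7.1.1), rechallenge is not applicable (Section 7.1.2) and withdrawn patients are not replaced (Section 6.3). In a three-period crossover, an early stop loses the patient's remaining periods and counts against the aim of at least 54 completers (Section 4.1). In the other direction, a patient whose reading meets one text but not the other stays on treatment. Cardiac effects and hypokalaemia are among the potential risks named in Section 2.3, and Appendix A 5 provides for no data monitoring committee, so application of this section at the sites matters.

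The ambiguity also reaches the analysis. Item 61 needs a definite answer on whether a withdrawal criterion was fulfilled, and Section 7.1 does not always give one.

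**Working it through.** The plan states no figure to reproduce here. The check compares the texts and then counts scheduled readings.

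**Step 1: windows side by side (Protocol Section 7.1)**

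| Criterion | Heading | Bullet | Relation |
|---|---|---|---|
| SBP | any time after randomisation | 12 h after dosing | bullet narrower |
| Potassium <3.0 mmol/L | any time after randomisation | 4 h after dosing | bullet narrower |
| QTcF >500 ms | 4 h after dosing | whole treatment period | bullet wider |
| QTcF change >60 ms | 4 h after dosing | 4 h after dosing | agree |

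**Step 2: can each pair be reconciled by reading?** For SBP and potassium, the heading can be taken as the span of the study covered and the bullet as the hours after a dose that count. That is a fair reading, but it is not stated. The haematology and liver bullets under heading (b) carry no window of their own, so for them that heading is the working window.

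For QTcF >500 ms, nesting would need the bullet to give the days and the heading the hours. The sentence does not fit this. It attaches the 4-hour limit in parentheses to the >60 ms limb alone. If the heading already imposed 4 hours on both limbs, the parenthesis would be redundant.

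**Step 3: scheduled readings in dispute.** The inputs are Protocol Table 1 footnotes g (blood pressure), h (ECG) and k (i-STAT). The count takes readings after the first dose of a period. Pre-dose readings on Days 8 and 14 are taken as about 24 h after the previous dose. Footnote u allows ±1 h on each daily dose, so consecutive doses are at least 24 − 2 = 22 h apart, and these readings fall well outside 12 h.

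- SBP: Day 1 at 1, 2, 4, 24 h (4), Day 8 pre-dose, 1, 4 h (3), Day 14 pre-dose, 1, 2, 4, 24 h (5). Total 4 + 3 + 5 = 12. Beyond 12 h: Day 1 24 h, Day 8 pre-dose, Day 14 pre-dose, Day 14 24 h = **4 of 12**.
- ECG: Day 1 at 1, 2, 4, 24 h (4), Day 8 at 1, 4 h (2), Day 14 pre-dose, 1, 2, 4, 24 h (5). Total 4 + 2 + 5 = 11. Beyond 4 h: Day 1 24 h, Day 14 pre-dose, Day 14 24 h = **3 of 11**.
- i-STAT potassium: Day 1 at 1, 2, 4, 24 h (4), Day 14 pre-dose, 1, 2, 4, 24 h (5). Total 4 + 5 = 9. Beyond 4 h: the same three times = **3 of 9**.

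Per period: 4 + 3 + 3 = 10. Over three periods: 3 × 10 = 30. The three 24-hour readings after the last Period 3 dose cannot stop treatment, so 30 − 3 = **27** per completing patient (SBP 11, ECG 8, i-STAT 8). Leaving out the 24-hour reading after the last dose of every period gives 3 + 2 + 2 = 7 per period, or 3 × 7 = 21.

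The Day 1 pre-dose readings are not counted. For SBP that reading is the reference value and cannot show a rise.

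**Step 4: which potassium test?** Footnote j schedules the safety laboratory at Visit 1, pre-dose on Day 1, 24 h after the Day 14 dose and at follow-up. Section 8.2.1 sends clinical chemistry, including the serum or plasma potassium in Table 8, to the central laboratory. No such sample is scheduled within 4 h of a dose; only i-STAT potassium is. The bullet names serum potassium and does not mention i-STAT.

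**Step 5: effect in the SAP.** Take a patient with a confirmed QTcF of more than 500 ms at 24 h on Day 1 who continues. Under the bullet, item 61 applies and the whole patient leaves the per-protocol set. Under the heading, item 61 does not apply and the patient stays.

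**The case against.** The strongest reply is that a specific bullet under a general heading is ordinary drafting, so the blood pressure and potassium criteria work as written. That stands in part. Those two pairs are ambiguous, not flatly contradictory, and what is missing is a statement of precedence. The reply does not rescue QTcF >500 ms, where the bullet is wider than its heading.

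A second reply is that no late abnormal reading goes unmanaged. Section 8 asks for immediate safety concerns to be discussed with the sponsor. Section 8.2.4 has the investigator judge whether the patient remains eligible. Section 7.1 lists adverse events and any other reason as grounds for stopping, requires a repeat test and encourages discussion with the study physician. This stands, and it means there is a route to stopping under either reading. It does not settle whether a criterion was met, which item 61 needs to know.

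A third reply is that the analytic effect is small. Item 61 touches only the per-protocol set, which serves as a sensitivity analysis of the primary endpoint, and the list of efficacy-relevant deviations is settled blind before unblinding. This is correct and limits the consequence.

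Two related points are not defects. Section 7.1 opens with "Patients may be discontinued from IP in the following situations", while the potassium bullet is mandatory. A permissive lead-in to a mixed list, with some firmer bullets, is workable. No blood pressure is scheduled between 4 and 24 h although the SBP window runs to 12 h, but unscheduled readings are possible during the overnight stays.

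**Conclusion.** The point holds, firmly for one limb and more weakly for two criteria. The QTcF >500 ms limb is internally inconsistent and affects 3 of 11 scheduled on-treatment ECGs per period. SBP (4 of 12) and i-STAT potassium (3 of 9) are ambiguous for want of stated precedence, and the potassium bullet does not name the test that falls in its window. In all, about 27 scheduled readings per completing patient can be classified either way, or 21 if the 24-hour reading after each period's last dose is left out. That exclusion bears on QTcF in particular: the treatment period is described as 14 days, so this ECG falls on Day 15, and without it the ECG count is 2 of 11. These figures count scheduled slots across different measures. The documents give no rate at which thresholds would be crossed, so the number of patients affected is unknown.

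A reader might infer more than the documents support:

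- That sites will act differently on the same reading. This is possible, but not shown.
- That the whole QTcF criterion is inconsistent. The >60 ms limb agrees with its heading at 4 hours.
- That these are the only numeric stopping rules for cardiac risk. Section 7.1(c) also has numeric heart-rate criteria.
- That late safety readings matter because the effect lasts 36 hours. That figure in Section 2.3 concerns bronchodilation after single doses of 400 and 1800 µg, not QTcF, potassium or blood pressure.

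The point still deserves action, because the rule decides who stops treatment irreversibly and the repair is cheap.

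**What to change.** In Protocol Section 7.1, reconcile heading and bullet so that the SBP, potassium and QTcF >500 ms criteria each have one stated window. Name the potassium test to which the criterion applies. Have SAP Section 2.2 and Table 1 item 61 refer to the reconciled text, so that whether a withdrawal criterion was fulfilled has one answer. Which window applies is a clinical decision for the medical team, and none is proposed here.

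The cost is wording in one protocol section and a cross-reference in the SAP. No added assessments are needed.
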